11.3 Adverse Drug Reaction (ADR)

An adverse drug reaction is a response to an investigational product which is noxious and unintended that which occurs in doses normally used in humans for prophylaxis, diagnosis or therapy of disease or for modification of physiological function.

The phrase "responses to an investigational product" means that a causal relationship between an investigational product and an adverse event is at least a reasonable possibility, i.e., the relationship cannot be ruled out.

The expression "causal relationship" is meant to convey that in general there are facts, evidence or arguments to suggest a reasonable causal relationship.

11.4 Serious Adverse Events (SAE)

A serious adverse event or reaction is any untoward occurrence that at any dose:

- 1. Results in death
- 2. Is life-threatening
- 3. Requires inpatient hospitalization or prolongation of existing hospitalisation,
- 4. Results in persistent or in significant disability/incapacity
- 5. Is a congenital abnormality or a birth defect

The term "life-threatening" in the definition of "serious" refers to an event in which the participant was at risk of death at the time of the event; it does not refer to an event which hypothetically might have caused death if it were more severe.

11.5 Serious Adverse Drug Reaction (SADR)

SADRs are any adverse events that have a causal relationship (i.e. possibly, probably, or definitely related) with the investigational product which are serious.

11.6 Serious and Unexpected Adverse Drug Reaction (SUADR)

SUADRs are SADR that are unexpected, where severity of which is not consistent with the applicable product information of each component of the paste and suspension.

All SUADRs will have expedited reporting to regulatory agencies following ICH-GCP and local regulatory requirements.

11.7 Assessment of all Adverse Events (including Serious Adverse Events)

11.7.1 Relationship (Causality/Relatedness)

The causality assessment is the determination, according to the site investigator's clinical judgment, of the existence of a reasonable possibility that the study drug (Investigational Product) caused or contributed to an adverse event.

If the site investigator or delegated sub-investigator is unsure about whether or not the study drug caused or is related to the event, then the event will be handled as "related" to the study drug for reporting purposes of the trial. If the causality assessment is "unknown but not related" to the study drug, this should be clearly documented in the source documents.

11.7.2 Expectedness

Events are classified as unforeseen or unexpected if the nature, severity or frequency is not consistent with the risk information set out in the product information or label of each component of the paste and suspension.

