7.2 Intervention group

All patients eligible for the intervention will receive the following in addition to the usual infection control measures:

- 1. A six-hourly topical application of 0.5g paste, containing colistin 10mg, tobramycin 10mg and nystatin 125,000 IU, to the buccal mucosa and oropharynx
- 2. A six-hourly administration of 10 mL of a suspension containing 100 mg colistin, 80 mg tobramycin and 2 x 10^6 IU nystatin, to the gastrointestinal tract via a gastric/post-pyloric tube
- 3. A four-day course of an intravenous antibiotic. Patients not already receiving a therapeutic antibiotic will be prescribed cefotaxime 1g six-hourly or ceftriaxone 1g daily, with dose adjusted as appropriate for organ dysfunction. Ciprofloxacin (400mg 12-hourly) may be used as an alternative if there is a contraindication to cephalosporins (e.g. allergy). Patients already receiving an alternative IV antibiotic to treat infection will not receive this additional intravenous antibiotic, but will continue the prescribed antibiotic for the usual duration of therapy.

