7.2.2 Provision of study drug

The George Institute for Global Health holds all intellectual property for the acquisition, manufacturing and distribution of the SuDDICU drug preparation for the conduct of the x-cRCT in Australia, Canada and the UK.

Under a legal agreement, the George Institute has contracted Verita Pharma[®], Sydney, Australia to acquire, manufacture, test and package the SuDDICU drug preparation according to Good Manufacturing Practice (GMP) standards, supplied in numbered patient-specific boxes to the ICUs / hospital pharmacies from a central store to sites in Australia.

Drug acquisition and distribution to Canada/UK will be provided by Verita Pharma[®] under licence from the George Institute.

The study paste and suspension will be constituted from GMP-certified suppliers of colistin, tobramycin and nystatin that are licensed antibacterial and antifungal drugs used in critically ill patients when indicated.

The study paste and suspension will be registered with the Australian Therapeutic Goods Administration, via the Clinical Trial Notification (CTN) process, Health Canada in Canada and the Medicines and Healthcare products Regulatory Agency (UK).

Copies of an Investigator's Brochure and study drug information sheets will be supplied to participating sites and updated as required.

Most of the intravenous antibiotics are considered standard practice and the only study specific intervention is an intravenous antibiotic (ceftriaxone/cefotaxime or ciprofloxacin) administered to the subset of patients not already treated with antibiotics for clinical purposes.

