10.1 Adverse Drug Reactions (ADR)

Regarding marketed medicinal products, a well-accepted definition of an adverse drug reaction is:

'A response to a drug which is noxious and unintended, and which occurs in doses normally used in humans for prophylaxis, diagnosis or therapy of disease or for modification of physiological function'.

Any adverse reaction thought to be study treatment related will be reported to the coordinating centre within 7 days of discovery.

The principal investigator will be responsible for determining the causal relationship as either possible, probable or definitely study treatment related.

Notification will be by fax, scanned document sent by email or by notification of a completed ADR form on the web-based data management system.

All adverse reactions will be reviewed by the coordinating centre staff and recorded in a safety database which will be monitored by the study management committee on a regular basis.

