11.7.5 Adverse Event Recording

Adverse events that are assessed and determined **not** to be related to the investigational product will not be recorded and reported.

In this study, recording and reporting of adverse events will be restricted to events that are assessed by the site investigator or delegated sub-investigators to be related to investigational product (i.e. possibly, probably or definitely related).

Investigations into potential adverse events should be done during each contact with a participant. Investigations may be done through specific questioning and, as appropriate, by examination. Information on all adverse events should be recorded promptly in the source document e.g. medical chart, progress notes, and assessed by the site investigator or delegated sub-investigators in a timely manner allowing sufficient time to meet required reporting timelines for AEs if needed. Only AEs that are related to the investigational product, regardless of seriousness, will be recorded on the study CRFs (e.g. adverse event

CRFs). Adverse event CRFs should be completed using source documents by a delegated research team member in a timely manner/within 15 days of site awareness. All clearly related signs, symptoms, and abnormal diagnostic procedures should be recorded in the source document, though should be grouped under one diagnosis. Each diagnosed adverse event should then be categorized in accordance with Medical Dictionary for Regulatory Activities (MedDRA) classifications.

If the site investigator or delegated sub-investigator is unsure about whether the event is caused by or related to the investigational product, then the event will be handled as "related" to the study drug for reporting purposes of the trial. If the causality assessment is "unknown but not related" to the investigational product, this should be clearly documented in the source documents.

The following are not considered AEs and therefore do not require recording:

- 1. Pre-existing diseases or conditions identified and recorded at screening/baseline unless, at the discretion of the site investigator, the disease or condition worsens in severity or frequency
- 2. At the discretion of the site investigator, events considered likely manifestations of the underlying disease or that commonly occur in the study population independent of investigational product exposure
- 3. Elective medical or surgical procedures.

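### The Canada/UK safety rules fix expectedness against the paste and suspension only and never say whether relatedness covers the study IV antibiotic, which is the third SDD component

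*Protocol*

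**What the plan says.** **The intervention.** Protocol section 7.2 lists three SDD components: the paste, the suspension and "A four-day course of an intravenous antibiotic". On the third it says "Patients not already receiving a therapeutic antibiotic will be prescribed cefotaxime 1g six-hourly or ceftriaxone 1g daily", with ciprofloxacin as the alternative when cephalosporins are contraindicated. Section 7.2.2 notes that most IV antibiotic use is ordinary practice, but adds that "the only study specific intervention is an intravenous antibiotic (ceftriaxone/cefotaxime or ciprofloxacin) administered to the subset of patients" who are not already being treated.

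**Safety rules, Canada/UK.** Section 11.7.2 makes an event unexpected when it "is not consistent with the risk information set out in the product information or label of each component of the paste and suspension", whether in kind, in severity or in how often it occurs. Section 11.6 defines the serious unexpected reaction (SUADR) by a severity "not consistent with the applicable product information of each component of the paste and suspension". Section 11.7.1 assesses causality against the study drug, glossed as the investigational product. Section 11.7.5 then says "Only AEs that are related to the investigational product, regardless of seriousness, will be recorded on the study CRFs", and section 11.8 excludes unrelated serious events from recording and reporting.

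**Safety rules, Australia.** Section 10.1 says "Any adverse reaction thought to be study treatment related will be reported to the coordinating centre within 7 days of discovery". Section 10.3 judges expectedness against the product information without naming any drug.

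**The concern.** The expectedness reference leaves out a drug that the trial itself assigns. The term that decides whether an event reaches the CRF is not defined in a way that settles whether that drug counts. Consider an SDD patient in Canada or the UK who has a serious reaction to study-assigned ceftriaxone or ciprofloxacin. The protocol offers two readings of investigational product, and neither handles this event properly.

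These doses are given because of the allocation, so reactions to them belong in the trial's safety record. Section 15.8 summarises expected SAEs and compares the proportions of patients with an SAE between arms. What is recorded, and what is called expected, therefore feeds those tables. The rule operates at the site when the event occurs, so an analysis plan cannot recover an event that was never entered on the CRF.

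**Working it through.** The protocol gives no figure to reproduce here. The check is a comparison of its sections, followed by a rough count of exposed patients.

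**1. Is the IV antibiotic part of the trial intervention?** Yes, in patients not already treated.
- Section 7.2 lists it as the third component, and section 7.2.2 calls it study specific in that subset.
- Section 7.2.1 places only systemic antibiotics continued for longer on clinical grounds outside the trial intervention.
- Sections 8.5 and 15.2.6 collect and analyse its delivery as part of SDD.

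**2. Is it in the expectedness reference for Canada/UK?** No. Sections 11.6 and 11.7.2 both name only the paste and suspension, whose active drugs are colistin, tobramycin and nystatin.

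**3. Is it in the investigational product?** The protocol does not say. Section 7.2.2 reads "The study paste and suspension will be registered with the Australian Therapeutic Goods Administration" and goes on to Health Canada and the UK regulator. The IV drugs are not named there, so a site could reasonably take the narrow reading.

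**4. Apply each reading to a reaction to the study IV antibiotic.**

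| Reading of investigational product | CRF entry and reporting | Expectedness |
|---|---|---|
| Narrow: paste and suspension | If confidently attributed to the IV drug alone, it is unrelated under 11.7.5 and 11.8: source documents only | Not reached |
| Broad: all three components | Captured | Judged against colistin, tobramycin and nystatin information |

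Under the broad reading, a reaction listed for the cephalosporin or quinolone but not for the paste and suspension drugs is classed as unexpected and gets expedited reporting under section 11.6. Less often, an event may be called expected only because a different drug lists it.

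**5. What is captured under either reading?**
- Every *C. difficile* infection, with no causality condition (sections 11.10 and 11.13).
- Events of unsure causality, which are handled as related (sections 11.7.1 and 11.7.5).

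**6. Scale of exposure.** Inputs:
- 7 Canadian + 3 UK ICUs = 10 (section 6.1).
- At least 150 patients per ICU per period; the Canada/UK row of the section 15.1 table is filled only at 200.
- 61% already on therapeutic antibiotics at ICU admission in the pilot (section 3.2.3), so 100% − 61% = 39% not.
- One SDD period per ICU.

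Exposed patients = ICUs × patients in the SDD period × share not already treated:
- 10 × 150 × 0.39 = 585
- 10 × 200 × 0.39 = 780

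This counts patients who could receive the drug. The protocol gives no rate for reactions attributed to it, so the number of affected events cannot be calculated.

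**The case against.** The case against is mainly that the consequences are easy to overstate, and much of it stands.

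- **Harms go unrecorded.** A reader might infer that reactions to the IV antibiotic are lost altogether. Section 11.7.5 sends all adverse events to source documents; only CRF entry and reporting depend on relatedness. Because doubtful causality defaults to related, the gap needs a confident attribution to the IV drug with the paste and suspension ruled out. *C. difficile* is covered separately, and section 15.8 compares deaths whatever the attribution.
- **Both readings are equally harmful.** They are not. Under the broad reading the event is captured, and the usual error is over-reporting.
- **The two regions capture different events.** A reader might infer this from the wording about study treatment in section 10. That section never defines the term, and section 10.4 asks about the relationship to the study drug, which is equally undefined. Section 10.3 does avoid the restriction to paste and suspension. A regional difference in capture is therefore possible but not shown.
- **A larger exposure count.** Using 250 patients per period would give 10 × 250 × 0.39 = 975, but the section 15.1 table has no Canada/UK entry at 250.
- **The scope may be deliberate.** The paste and suspension are the products section 7.2.2 says will be registered, and most IV antibiotic use is standard practice. That may explain the wording. It does not justify it for doses that the same section calls study specific.

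**Conclusion.** The concern holds as a faulty stated rule with limited consequences. For Canada and the UK, the expectedness reference omits a study-assigned drug, and relatedness rests on a term whose scope is not stated. Depending on the reading, a reaction to the study IV antibiotic is either kept off the CRF when attributed to that drug alone, or captured and judged against the wrong product information.

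The exposed group is roughly 585 to 780 patients. That rests on the pilot's share at ICU admission carrying over to enrolment, which can come later, and on every untreated SDD patient receiving the drug. The size of any effect on the safety tables is unknown. The primary mortality analysis does not depend on this point. The change is worth making because these are harms of an assigned component and the remedy is cheap.

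**What to change.** 1. In sections 11.6 and 11.7.2, extend the reference to include the product information of the study-assigned IV antibiotic that the patient received.
2. In sections 11.7.1, 11.7.5 and 11.8, state that relatedness for recording and reporting covers all three SDD components. This can be done without reclassifying the IV antibiotic as a registered investigational product.
3. Use the same scope wording in section 10, so that the regions apply one rule before the databases are merged.
4. If Canada/UK recruitment is already complete, state in the safety report which reading the sites applied.

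The cost is a protocol wording change and a note to sites. A few more related events may be recorded. No treatment rule or study procedure changes, and the primary outcome analysis is unaffected.

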11.7.3 Seriousness

Events are classified as serious if associated with effects threatening the life or physiological functions of a participant. Refer to the definition above for "Serious Adverse Events".

11.7.4 Severity

The term "severe" is often used to describe the intensity (severity) of a specific event (e.g. mild, moderate, or severe myocardial infarction); the event itself, however, may be of relatively minor medical significance (such as severe headache).

This is not the same as "serious," which is based on participant/event outcome or action criteria usually associated with events that pose a threat to a participant's life or functioning. The terms "serious" and "severe" are not synonymous. Seriousness (not severity) serves as a guide for defining regulatory reporting obligations.

11.7.5 Adverse Event Recording

Adverse events that are assessed and determined **not** to be related to the investigational product will not be recorded and reported.

In this study, recording and reporting of adverse events will be restricted to events that are assessed by the site investigator or delegated sub-investigators to be related to investigational product (i.e. possibly, probably or definitely related).

Investigations into potential adverse events should be done during each contact with a participant. Investigations may be done through specific questioning and, as appropriate, by examination. Information on all adverse events should be recorded promptly in the source document e.g. medical chart, progress notes, and assessed by the site investigator or delegated sub-investigators in a timely manner allowing sufficient time to meet required reporting timelines for AEs if needed. Only AEs that are related to the investigational product, regardless of seriousness, will be recorded on the study CRFs (e.g. adverse event

CRFs). Adverse event CRFs should be completed using source documents by a delegated research team member in a timely manner/within 15 days of site awareness. All clearly related signs, symptoms, and abnormal diagnostic procedures should be recorded in the source document, though should be grouped under one diagnosis. Each diagnosed adverse event should then be categorized in accordance with Medical Dictionary for Regulatory Activities (MedDRA) classifications.

If the site investigator or delegated sub-investigator is unsure about whether the event is caused by or related to the investigational product, then the event will be handled as "related" to the study drug for reporting purposes of the trial. If the causality assessment is "unknown but not related" to the investigational product, this should be clearly documented in the source documents.

The following are not considered AEs and therefore do not require recording:

- 1. Pre-existing diseases or conditions identified and recorded at screening/baseline unless, at the discretion of the site investigator, the disease or condition worsens in severity or frequency
- 2. At the discretion of the site investigator, events considered likely manifestations of the underlying disease or that commonly occur in the study population independent of investigational product exposure
- 3. Elective medical or surgical procedures.

11.8 Reporting of SAEs and Unanticipated Events

Serious adverse events and unanticipated events that are assessed and determined **not** to be related to the investigational product **will not** be recorded and reported.

11.9 Investigator reporting: Notifying the REB

Serious adverse events and unanticipated events should be recorded and reported to the REB by the site investigator in accordance with local reporting requirements and timelines.

11.10 Investigator reporting: Notifying the Canadian Sponsor

The site investigator is responsible for reporting SAEs and SUADRs to the sponsor in accordance with applicable regulations and reporting requirements and timelines.

Serious and unexpected events that are related or cannot be ruled out as related to the investigational product are considered SUADRs. Reporting for SUADRs should include a description of the event in sufficient detail to allow for a complete medical assessment of the case and independent determination of possible causality. The minimum information required includes at least one identifiable participant, one identifiable reporter, one serious reaction, and one suspect product.

Additionally, serious adverse events that are both related and unexpected, CIOMS I Form must be completed by the site investigator and forwarded to the Sponsor at [contact] within 24 hours of site awareness. Information on other possible causes of the event, such as concomitant medications and illnesses should also be provided as soon as it is made available.

Information on all serious adverse events should be recorded promptly in the source document e.g. medical chart, progress notes, and assessed by an investigator in a timely manner allowing sufficient time to meet required reporting timelines for SAEs and serious and unexpected adverse drug reaction (SUADRs) if needed (see below).

All cases of *Clostridioides Difficile* infections will be recorded on the study CRFs and reported to the Sponsor as a SAE within 72 hours.

11.11Sponsor Reporting of SUADRs: Notifying Health Canada

The regulatory sponsor is responsible for reporting SUADRs to regulatory authorities in accordance with local expedited reporting requirements and timelines. In addition, the Sponsor will complete the ADR Expedited Reporting Summary Form and submit this form in conjunction with the completed CIOMS Form to the appropriate Health Canada directorate.

11.12 Sponsor Reporting of SUADRs: Notifying Sites

The regulatory sponsor is responsible for distributing blinded expedited reports of SUADRs to each investigator within 15 days of sponsor awareness.

11.13Reporting and Entry Timelines

The site investigator will report SAEs to the sponsor within the following timelines:

- 1. All deaths and immediately life-threatening events, related, will be recorded on the CRF and reported to the sponsor within 24 hours of site awareness.
- 2. Serious adverse events other than death and immediately life-threatening events will be reported to the sponsor within 72 hours of site awareness.
- 3. All cases of *Clostridioides Difficile* infections will be reported to the sponsor within 72 hours of site awareness.

SADR and SUADR information and all cases of *Clostridioides Diff*icile infections will be entered into the CRF in a timely manner/within 72 hours from the time the site investigator becomes aware of the event.

12 Ethics and dissemination

The study will be performed in accordance with ethical principles consistent with the Declaration of Helsinki and all relevant national and local guidelines on the ethical conduct of research.

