10.2 Serious Adverse Drug Reactions (SADRs)

Serious adverse *events* are defined as any untoward medical occurrence that meets one of more of the following criteria:

- 1. Results in death
- 2. Is life-threatening
- 3. Requires inpatient hospitalisation or prolongation of existing hospitalisation
- 4. Results in persistent or significant disability/incapacity
- 5. Is a congenital anomaly/birth defect

The classification of 'serious adverse event' is not related to the assessment of the severity of the adverse event. An event that is mild in severity may be classified as a serious adverse event based on the above criteria. Given that critically ill patients are likely to experience any of the above listed criteria in the course of their ICU admission, only serious events that are thought to be study treatment related will be reported.

Serious adverse drug reactions should be reported to the coordinating centre within 24-hours of participating site study staff becoming aware of the occurrence. A member of the coordinating centre will be on call 24-hours a day via mobile phone for out of 'business hours' reporting.

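### Sections 11.10 and 11.13 set unreconciled site-to-sponsor deadlines (24 and 72 hours) for a related, unexpected serious event that is not fatal or immediately life-threatening

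*Protocol*

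**What the plan says.** Section 11 of the protocol covers safety reporting in Canada and the UK. Two of its subsections set deadlines for the site investigator to inform the sponsor.

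Section 11.10 first defines the class: "Serious and unexpected events that are related or cannot be ruled out as related to the investigational product are considered SUADRs". It then adds a duty for that class: "serious adverse events that are both related and unexpected, CIOMS I Form must be completed by the site investigator and forwarded to the Sponsor", to be done "within 24 hours of site awareness". Neither sentence is limited to fatal or life-threatening events. A later paragraph of 11.10 asks for records and assessments to be prompt enough to meet "required reporting timelines for SAEs and serious and unexpected adverse drug reaction (SUADRs) if needed (see below").

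Section 11.13 is the list of site-to-sponsor timelines for serious adverse events. Item 1 gives 24 hours for related deaths and related immediately life-threatening events. Item 2 covers the remainder: "Serious adverse events other than death and immediately life-threatening events will be reported to the sponsor within 72 hours of site awareness". Item 3 gives 72 hours for *Clostridioides difficile* infections, which agrees with 11.10. The list does not mention SUADRs; they appear only in the closing sentence, on CRF entry.

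**The concern.** A SUADR that is serious only because, for example, it prolongs hospitalisation falls under both the 24-hour rule of 11.10 and the 72-hour rule of 11.13 item 2. The reporter, the recipient and the starting point are the same, but the limits are not, and the protocol does not say that one section overrides the other.

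The layout increases the risk that the shorter limit is missed. Section 11.10 sends the reader onward for SUADR timelines. The only later place that sets site-to-sponsor limits for serious events in general is 11.13, which does not repeat the 24-hour rule.

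Two later steps depend on the site's report. Under 11.11, the sponsor submits the completed CIOMS form to Health Canada with its own summary form. Under 11.12, the sponsor has 15 days from its own awareness to notify the other investigators. A late site report delays both. Monitors would also have two standards for deciding whether a report was late.

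**Working it through.** No sample size, power or error rate is involved. The check compares the two rules by class of event and looks for any text that limits or ranks them.

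**Inputs**
- 11.10: related and unexpected serious event, CIOMS I form to the sponsor, 24 hours from site awareness.
- 11.13 item 1: related death or immediately life-threatening event, 24 hours from site awareness.
- 11.13 item 2: every other serious adverse event, 72 hours from site awareness.
- 11.7.5 and 11.8: events judged unrelated are not recorded or reported, so item 2 applies to related events.
- 11.4: hospitalisation or its prolongation is enough to make an event serious, so an event can be serious without being fatal or life-threatening.
- 11.12: notice to investigators within 15 days of sponsor awareness.
- 6.1: 7 ICUs in Canada and 3 in the UK, so 7 + 3 = 10 ICUs work under section 11.

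**Comparison for related serious events** (*C. difficile* infections left out, since both sections give them 72 hours)

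| Class | 11.10 | 11.13 | Difference |
|---|---|---|---|
| Fatal or immediately life-threatening, unexpected | 24 h | 24 h | 0 h |
| Fatal or immediately life-threatening, expected | no specific limit | 24 h | no conflict |
| Other serious, expected | no specific limit | 72 h | no conflict |
| Other serious, unexpected | 24 h | 72 h | 72 − 24 = 48 h |

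Only the last class has two different limits. It is not empty, given 11.4, and item 2 does not exclude it.

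**Effect on the cross-site notice.** If the site reports at its limit and the sponsor uses its full 15 days, other investigators hear at most 1 + 15 = 16 days after site awareness under 11.10, and 3 + 15 = 18 days under 11.13 item 2. The difference is 2 days per event.

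**Precedence.** Neither section names the other as governing, and item 2 carries no exception. The onward reference in 11.10 stands in a paragraph on source recording and assessment. It does not withdraw the 24-hour rule, but it does send the reader to a list that omits it.

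**The case against.** The strongest reply is that the rules are layered. Section 11.10 introduces the CIOMS form as an additional duty, with its own form and its own deadline, for a narrower class of event. On that reading 11.13 is the general rule for serious events and 11.10 the specific rule for SUADRs. Both limits are maxima, so a report within 24 hours satisfies both. This stands, and it rules out the stronger claim that a site can comply with the protocol and still report late: a site that sends a SUADR at 72 hours has broken 11.10. What remains is that the protocol never states the layering and that the list itself leaves the SUADR limit out.

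A reader might infer three further faults, which the documents do not support:

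- **CRF entry.** Section 11.13 allows 72 hours to enter SUADR information in the CRF. Data entry and forwarding a CIOMS form are different acts, so this limit does not contradict 11.10.
- **Australia.** Section 10.2 states: "Serious adverse drug reactions should be reported to the coordinating centre within 24-hours". Sections 10 and 11 are separate regional systems run by separate sponsors, so a different limit in one region contradicts nothing in the other.
- **Regulatory clock.** The protocol starts the 15-day notice to investigators from sponsor awareness. For the regulator, 11.11 refers only to local requirements and gives no starting point. What the text supports is that the submission needs the completed CIOMS form, not that a regulatory deadline would be missed.

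It is also an assumption that sites would work from 11.13 alone. The section's heading and the onward reference in 11.10 make this plausible, but the protocol does not direct it.

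**Conclusion.** This is an internal inconsistency in the safety-reporting text, wrong as written and minor. It affects one class of event: related, unexpected and serious, but neither fatal nor immediately life-threatening. For that class a site at any of the 10 Canadian and UK ICUs that relied on 11.13 alone could inform the sponsor up to 48 hours later than 11.10 requires.

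The 48 hours is a maximum per event. It assumes that the site overlooks the CIOMS sentence in 11.10 and uses the full 72 hours. The protocol gives no expected number of SUADRs, so a total effect cannot be estimated. Fatal and immediately life-threatening related events have 24 hours under 11.13 in any case. The primary mortality analysis is not touched.

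**What to change.** Reconcile 11.10 and 11.13 so that one site-to-sponsor deadline for SUADRs, chosen by the sponsor, appears in both. Either of two edits would do this: a separate SUADR line in the 11.13 list, or an exception in item 2 that refers to 11.10. Replacing the general onward reference in 11.10 with the section number would remove the remaining doubt.

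The cost is one line in an administrative amendment and a note to the Canadian and UK sites. No data collection or analysis changes.
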